7.3. Lost to follow-up

A participant will be considered 'lost to follow-up' if he/she fails to return for scheduled visits and cannot be contacted by the study site.

Please refer to the SPM for a description of actions to be taken before considering the participant lost to follow-up.

Study conclusion call/visit and discontinuation of individual sites or of the study as a whole is described in Section [10.1.9](#).

8. STUDY ASSESSMENTS AND PROCEDURES

Protocol waivers or exemptions are only permitted when necessary for the management of immediate safety concerns for the participant.

Immediate safety concerns should be discussed with the sponsor as soon as they occur or when the study team becomes aware of them. The purpose of this communication is to determine if the participant(s) should discontinue the study intervention.

Study procedures and their timing are summarised in the SoA (Section [1.3](#)).

All screening evaluations must be completed and the results reviewed before confirming that potential participants meet all eligibility criteria. Refer to Sections [8.2.1.2](#) and [8.2.1.3](#) for details on screening evaluations in this study. Note: The safety laboratory evaluations in Phase I are not part of the screening evaluation in this study.

The investigator will maintain a log of all participants screened. All relevant information, such as confirmation of eligibility and reasons for screening failure will be mentioned in this screening log.

Procedures conducted as part of routine clinical management (e.g. haematologic profiles), and obtained before the participant/participant's parent(s)/LAR(s) signed the Informed Consent Form (ICF), may be used for screening and/or for establishing a clinical baseline (provided the procedure met protocol specified criteria and was performed within the time frame defined in the SoA (Section [1.3](#)).

The SPM provides the investigator and site personnel with detailed administrative and technical information that does not impact participant safety.

Decentralised study procedures (Phase II only):

If local regulations allow and quality of study procedures is maintained, participant(s) can be offered remote visits (e.g. telemedicine, home visits) for the collection of biological samples and/or safety data/safety assessment(s)/study intervention administration. These remote visits must be performed by qualified study staff/healthcare professionals HCPs.

Refer to the Schedule of Activities for the timing of these visits. Details of how these visits will be conducted are outlined in the SPM.

Following procedures can be performed remotely/ virtually (with the exception of Visit 1 which is always a clinic visit). Refer to the [Glossary of terms](#) for definitions of telemedicine, remote and virtual visits:

- Safety follow-up may be performed by telemedicine which will use secure video conferences, phone calls, and a web portal and/or mobile application as a way of communicating with the participant and monitoring the participant's progress. In addition, qualified study staff/HCPs may also identify AEs and report them to the investigator for evaluation.
- Biological samples may be collected remotely by qualified study staff/HCPs. Biological samples should be collected only if they can be processed in a timely manner and appropriately stored until the intended use.
- Administration of study intervention can be performed remotely/at participant's home by qualified study staff/HCPs if appropriate storage conditions for the study intervention can be ensured. Furthermore, appropriate medical treatment must be readily available during 30 minutes after dosing in case of anaphylaxis, syncope.

Study procedures in special circumstances:

(Amended 22 March 2022)

During special circumstances (e.g., COVID-19 pandemic), the specific guidance from local public health and other competent authorities regarding the protection of individuals' welfare must be applied. For the duration of such special circumstances, the following measures may be implemented for enrolled participants:

- If the eDiary device was provided to the participant, it may be returned to the site by conventional mail after the end of the relevant data collection period (Visit 4 for Phase I, Visit 5 for Phase II, Formulation and Schedule-finding and Visit 3 for Phase II, Sourcing).
- Biological samples may be collected at a different location* other than the study site or at participant's home. Biological samples should not be collected if they cannot be processed in a timely manner or appropriately stored until the intended use.
- Phase II only (not applicable for Visit V1): Study visits may be performed at a different location* other than the study site (e.g. at participant's home). For study visits involving blood draw, biological samples should not be collected if they cannot be processed in a timely manner or appropriately stored until the intended use.
- If despite best efforts it is not possible to collect the biological samples within the interval pre-defined in the protocol (see [Table 2](#) for Phase I, [Table 4](#) for Phase II, Formulation and Schedule-finding and [Table 8](#), [Table 9 and Table 10](#) for Phase II, Sourcing), then the applicable intervals may be extended up to a maximum length of days as presented in [Table 19](#) (Phase I), [Table 20](#) (Phase II, Formulation and

Schedule-finding) and **Table 21**, **Table 22 and Table 23** (Phase II, Sourcing), as applicable.

- If despite best efforts it is not possible to administer the dose of study intervention as defined in the protocol (see **Table 2** for Phase I, **Table 4** for Phase II, Formulation and Schedule-finding and **Table 8**, **Table 9 and Table 10** for Phase II, Sourcing), a maximum dose interval may be used as presented in **Table 19** (Phase I) and **Table 20** (Phase II, Formulation and Schedule-finding) and **Table 21**, **Table 22 and Table 23** (Phase II, Sourcing), as applicable.

* It is the investigator's responsibility to identify an alternate location. The investigator should ensure that this alternate location meets International Council on Harmonisation (ICH) GCP requirements, such as adequate facilities to perform study procedures, appropriate training of the staff and documented delegation of responsibilities in this location. This alternate location should be covered by proper insurance for the conduct of study on participants by investigator and staff at a site other than the designated study site.

** In case of home visits (for Phase II only), the study procedures should be carried out by a qualified person/s as delegated by the Principal Investigator, provided that the compliance with protocol procedures are ensured. Refer to Schedule of Activities for the schedule of visits (see **Table 3** and **Table 5**).

Refer to local regulations on the conduct of clinical trials during the COVID-19 pandemic for more details.

Impact on the per protocol set for immunogenicity will be determined on a case by case basis.

Table 19 Intervals between study visits/contacts during special circumstances – Phase I

Interval	Length of interval	Allowed interval (Visit window)
Visit V3 → Visit V4	30 days	23 to 51 days (-7 to +21 days)
Visit V3 → Telephone contact T2	120 days	113 to 141 days (-7 to +21 days)
Visit 3 → Telephone contact T3	180 days	173 to 201 days (-7 to +21 days)

Table 20 Intervals between study visits during special circumstances – Phase II Formulation and Schedule finding

Interval	Length of interval	Allowed interval (Visit window)
Visit V1 → Visit V2	30 days	23 to 51 days (-7 to +21 days)
Visit V1 → Telephone contact T2	90 days	83 to 111 days (-7 to +21 days)
Visit V2 → Visit V3/TC*	90 days	83 to 111 days (-7 to +21 days)
Visit V3/TC* → Visit V4	60 days	53 to 81 days (-7 to +21 days)
Visit V4 → Visit V5	30 days	23 to 51 days (-7 to +21 days)
Visit V4 → Telephone contact T3	90 days	83 to 111 days (-7 to +21 days)
Visit V4 → Telephone contact T4	180 days	173 to 201 days (-7 to +21 days)
Visit V4 → Telephone contact T5	270 days	263 to 291 days (-7 to +21 days)
Visit V4 → Visit V6	360 days	353 to 381 days (-7 to +21 days)

* Visit for **E** groups (Visit V3) and telephone call for Control group (TC)

Table 21 Intervals between study visits/contacts during special circumstances – Phase II (Sourcing; 0,1 month vaccination schedule)

Interval	Length of interval	Allowed interval (Visit window)
Visit V2 → Visit V3	30 days	23 to 51 days (-7 to +21 days)
Visit V2 → Telephone contact T1	120 days	113 to 141 days (-7 to +21 days)
Visit V2 → Telephone contact T2	180 days	173 to 201 days (-7 to +21 days)

Table 22 Intervals between study visits/contacts during special circumstances – Phase II (Sourcing; 0,2 month vaccination schedule)

Interval	Length of interval	Allowed interval (Visit window)
Visit V2 → Visit V3	15 days	8 to 22 days (-7 to +7 days)
Visit V2 → Visit V4	30 days	25 to 51 days (-5 to +21 days)
Visit V2 → Telephone contact T2	120 days	113 to 141 days (-7 to +21 days)
Visit V2 → Telephone contact T3	180 days	173 to 201 days (-7 to +21 days)

Table 23 Intervals between study visits/contacts during special circumstances – Phase II (Sourcing; 0,6 month vaccination schedule)

Interval	Length of interval	Allowed interval (Visit window)
Visit V2 → Visit V3	15 days	8 to 22 days (-7 to +7 days)
Visit V2 → Visit V4	30 days	25 to 51 days (-5 to +21 days)
Visit V2 → Telephone contact T2	120 days	113 to 141 days (-7 to +21 days)
Visit V2 → Telephone contact T3	180 days	173 to 201 days (-7 to +21 days)

8.1. Effectiveness and/or immunogenicity assessments

Biological samples will be used for research planned in the protocol and for purposes related to the improvement, development and quality assurance of the laboratory tests described in this protocol.

Findings in this or future studies may make it desirable to use samples acquired in this study for research not planned in this protocol. In this case, all participants in countries where this is allowed will be asked to give consent to allow GSK or a contracted partner, to use the samples for further research. The further research will be subject to prior Independent Ethics Committee/ Institutional Review Board (IEC/IRB) approval, if required by local legislation.

Information on further research and its rationale can be obtained from GSK.

Sample testing will be done in accordance with the recorded consent of the individual participant/participant's parent(s)/LAR(s).

By default, collected samples will be stored for a maximum of 20 years. This storage period begins when the last participant performs the last study visit. This timeline can be adapted based on local laws, regulations or guidelines requiring different timeframes or procedures. In all cases, the storage period should be aligned with participant's consent. These additional requirements must be formally communicated to, discussed and agreed with GSK.

8.1.1. Biological samples

8.1.1.1. Blood sample

(Amended 22 March 2022)

Phase I: An overall blood volume of approximately 240 mL per participant will be collected over the course of the Phase I part of the study. An additional 7 mL of blood will be collected at Visit V1 and Visit V2 from all participants for the safety laboratory evaluation. Refer to [Table 24](#) for details.

Table 24 Blood samples at Phase I

Sample type	Quantity	Unit	Timepoint	Subset name/ Group	Day
Blood	Approximately 80	mL	Visit V1 (CCI [REDACTED]);	All participants	Day 1
Blood	Approximately 80	mL	Visit V3 (CCI [REDACTED]);	All participants	Day 31
Blood	Approximately 80	mL	Visit V4 (CCI [REDACTED])	All participants	Day 61
Blood	Approximately 7	mL	Visit V1	All participants	Day 1
Blood	Approximately 7	mL	Visit V2	All participants	Day 8

Pre-Vacc, Pre-vaccination timepoint; Post-Vacc, Post-vaccination timepoint

Refer to [Table 1](#) (SoA for Phase I) for details of visits.

Phase II (sourcing): An overall blood volume of approximately 285 mL per participant will be collected over the course of the Phase II, Sourcing part of the study. Please refer to [Table 25](#) and [Table 26](#) for details.

Table 25 Blood samples at Phase II (Sourcing; 0,1 month vaccination schedule)

Sample type	Quantity	Unit	Timepoint	Subset name/ Group	Day
Blood	Approximately 95	mL	Visit V1 (CCI [REDACTED]);	All participants	Day 1
Blood	Approximately 95	mL	Visit V2 (CCI [REDACTED])	All participants	Day 31
Blood	Approximately 95	mL	Visit V3 (CCI [REDACTED])	All participants	Day 61

Pre-Vacc, Pre-vaccination timepoint; Post-Vacc, Post-vaccination timepoint

Refer to [Table 5](#) (SoA for Phase II, Sourcing) for details of visits.

Table 26 Blood samples at Phase II (Sourcing; 0,2 and 0,6 month vaccination schedule)

Sample type	Quantity	Unit	Timepoint	Subset name/ Group	Day
Blood	Approximately 95	mL	Visit V1 (CCI [REDACTED]);	All participants	Day 1
Blood	Approximately 95	mL	Visit V3 (CCI [REDACTED]);		Day 76
					Day 196
					Day 91
Blood	Approximately 95	mL	Visit V4 (CCI [REDACTED])		Day 211

Pre-Vacc, Pre-vaccination timepoint; Post-Vacc, Post-vaccination timepoint.

Refer to [Table 6](#) and [Table 7](#) (SoA for Phase II, Sourcing) for details of visits.

Note: the total number of participants (healthy adults) planned to be enrolled in the Phase I and Phase II (Sourcing) is required in order to collect sufficient serum samples for the development of assays to be used in the CCI vaccine clinical development program. All participants will be followed for safety up to 6 months after the last vaccination.

Phase II (formulation and schedule-finding): In order to provide the necessary serum volume for the bactericidal assays (enc-hSBA and/ or hSBA), an overall blood volume of approximately 90mL, per participant, will be collected over the course of the Phase II step of the study. Please refer to [Table 27](#) for details.

Table 27 Blood samples at Phase II (Formulation and schedule-finding)

Sample type	Quantity	Unit	Timepoint	Subset name/ Group	Day
Blood	Approximately 15	mL	Visit V1 (*)	All participants	Day 1
Blood	Approximately 15	mL	Visit V2 (**)	All participants	Day 31
Blood	Approximately 30	mL	Visit V5 (CCI)	All participants	Day 211
Blood	Approximately 30	mL	Visit V6 (^)	All participants	Day 541

* Pre-vaccination (Pre-Vacc) for C and Control groups

** Pre-vacc timepoint for C groups. For rest of the groups, C and Control, this is post-vaccination (post-Vacc 1) timepoint

^ Blood sample will be used only for assessment of tertiary objectives

Note: in case of local regulations limiting the amount of blood to be taken in the younger population (e.g 10-12 years of age and/or at the lower bound of the percentile of the growth chart), a reduced amount of blood volume could be drawn at Phase II, Visit 5 and Visit 6. In this population every effort must be done to collect at least 25mL of blood volume, samples will be analysed according to priority ranking provided in [Table 29](#) and [Table 30](#).

Refer to [Table 3](#) (SoA for Phase II, Formulation and Schedule-finding) for details of visits.

Insufficient blood volume may lead to test cancellation and jeopardise the statistical power. Hence, every effort must be done to collect blood volume as per protocol requirements.

Note 1: Blood samples are taken from all participants in Phase I and II irrespective of the testing status to maintain the blind of the study. Refer to Section [8.1](#) for details on how the unused/ left-over samples will be used.

Note 2: Check criteria for blood draw delay as specified in Section [5.5](#). A topical anaesthetic (e.g. EMLA adhesives or cream) may be used at the site of blood sample draw, according to local practice in order to minimise pain.

8.1.1.2. Urine sample

Urine samples for pregnancy testing will be collected from female participants of childbearing potential prior to the study intervention. Refer to Section [4.1](#) and [8.2.1.4](#) for details.

8.1.2. Laboratory assays

(Amended 22 March 2022)

All laboratory testing will be performed at GSK laboratory or in a laboratory designated by GSK. Refer to Section 8.1.1.1 for details on blood sampling.

Effectiveness of the CCI antigens of the CCI vaccine will be evaluated with serum bactericidal assays using endogenous source of human complement (enc-hSBA), on a panel of 110 US representative *N. meningitidis* serogroup B invasive disease strains. Immunogenicity of the vaccine against serogroups A, B, C, W and Y will be evaluated with the serum bactericidal assay using exogenous source of human complement (hSBA). An CCI *multiplex assay* will be used to evaluate the serotype-specific IgG responses to A, C, W, and Y.

Table 28 Laboratory assays – Phase I and II

CCI
REDACTED

Please refer to the Section 10.2 for a brief description of the assays performed in the study.

The addresses of clinical laboratories used for sample analysis are provided in a separate document accompanying this study protocol.

[figure not shown]
CONFIDENTIAL

212458 (MENACWY=CCI -001 PRI)

Protocol Amendment 4 Final

GSK clinical laboratories have established a Quality System supported by procedures.
The activities of GSK clinical laboratories are audited regularly for quality assessment by
an internal (sponsor-dependent) but laboratory-independent Quality Department.

C

[figure not shown]

CONFIDENTIAL

[figure not shown]
212458 (MENACWY=CCI -001 PRI)

Protocol Amendment 4 Final

CCI

CCI

[figure not shown]

CONFIDENTIAL

[figure not shown]
212458 (MENACWY=CCI -001 PRI)

Protocol Amendment 4 Final

CCI

CCI

CCI

8.1.4. Clinical safety laboratory assessments

Refer to the Section 10.2.1 for the list of clinical laboratory safety assessments required by the protocol. These assessments must be conducted according to the clinical laboratory manual and the SoA.

8.1.5. Immunological correlates of protection

No generally accepted immunological correlate of protection has been demonstrated so far against *N. meningitidis* serogroups A, B, W, and Y.

An hSBA titre ≥ 4 is a generally accepted correlate of protection against IMD caused by *N. meningitidis* serogroup C.

The immunological assay results will be communicated to the investigator when ready and available. Refer to Section 6.6 for details regarding treatment for non-responders.

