4.1.2.1. Phase II: Formulation and Schedule-finding

Phase II (Formulation and Schedule-finding) will include 5 study groups, with a staggered enrolment (45 participants for safety lead-in and 955 participants thereafter) of a total of 1000 participants ([Figure 2](#)):

- **CCI** Participants will receive 2 vaccinations of the **CCI** vaccine in a (0,6-months) schedule.
- **CCI**: Participants will receive 2 vaccinations of the **CCI** vaccine in a (0,2-months) schedule.
- **CCI** Participants will receive 2 vaccinations of the **CCI** vaccine in a (0,6-months) schedule.
- **CCI**: Participants will receive 2 vaccinations of the **CCI** vaccine in a (0,2-months) schedule.

[figure not shown]
The above 4 groups will also receive 1 injection of placebo, according to the schedule described in [Figure 2](#).

- **Control:** Participants will receive 2 vaccinations of MenB vaccine (*Bexsero*) in a (0,6-months) schedule and a single vaccination of MenACWY vaccine (*Menveo*).

For more detailed information on study groups and treatments administered, refer to [Table 13](#) and [Table 16](#).

The schedule of activities in Phase II (Formulation and Schedule-finding) of the study is described in [Table 3](#).

Figure 2 Study design overview – Phase II (Formulation and Schedule-finding)

CONFIDENTIAL

212458 (MENACWY=CCI -001 PRI)
Protocol Amendment 4 Final

Abbreviation: N, number of participants; V, clinic visit; D, day; TC, Telephone contact for Control group only; iSRC, internal safety review committee; PC, phone contact; BS, blood sample.

[^] The phone call at Day 8 is only for the first 45 participants (15 participants in CCI [REDACTED], 5 participants in CCI [REDACTED] 15 participants in CCI [REDACTED] 5 participants in CCI [REDACTED] and 5 participants in the Control groups).

* The outcome of the iSRC will impact the next study intervention at Month 4. The Month 1 blood sampling will proceed as planned.

Note 1: Blood draw at Visit 6 Month 18 will be used only for assessment of tertiary objectives.

Note 2: This figure represents the main aspects of the study design. Refer to [Table 3](#), Schedule of activities, for details on all visits and contacts

Note 3: The Phase II (Formulation and Schedule-finding) is partially blinded. Study conduct and data collection in groups C [REDACTED] [REDACTED] will be observer-blind while in group Control it will be open-label.

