Table 14 Study groups, intervention and blinding – Phase II (Sourcing)

Study groups	Number of participants	Age (Min-Max)	Study intervention(s)	Blinding
107				
60				
60				
60				
60				

* Due to the different vaccination schedules in Phase II Sourcing, the study will be observer blind only in terms of the vaccine formulations.

Duration of the Phase II (Sourcing) of the study: The intended duration of the Phase II (sourcing) of the study, per participant is:

- approximately 7 months *for the* [REDACTED] *and* [REDACTED] *groups*,
- *approximately 8 months for the* [REDACTED] *and* [REDACTED] *groups, and,*
- *approximately 12 months for the* [REDACTED] *and* [REDACTED] *groups.*

Data collection: Standardised Electronic Case Report Form (eCRF). Solicited events will be collected using a participant diary (electronic Diary [eDiary]).

Sampling schedule for Phase II (Sourcing) of the study:

- Blood sample: Refer to Section 8.1.1.1 for details on collection of blood samples.
- Urine sample: Urine samples for pregnancy testing will be collected from female participants of childbearing potential prior to the study intervention (*at the following timepoints*):
 - *at Visit 1 (Day 1) and Visit 2 (Day 31) for the* [REDACTED] *and* [REDACTED] *groups,*
 - *at Visit 1 (Day 1) and Visit 2 (Day 61) for the* [REDACTED] *and* [REDACTED] *groups, and,*
 - *at Visit 1 (Day 1) and Visit 2 (Day 181) for the* [REDACTED] *and* [REDACTED] *groups.*

The **primary completion date** for the study is the Day 541, Month 18 timepoint in Phase II. Refer to Section 9.4.6 for the planned interim analysis.

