4.4. End of Study definition

(Amended 22 March 2022)

A participant is considered to have completed the study if he/she returns for the last visit or is available for the last scheduled contact/ visit as described in the protocol /Telephone T3 in Phase I, Visit V6 in Phase II, Formulation and Schedule-finding and Telephone T2 or Telephone T3 in Phase II, Sourcing *(as per the group allocation)*.

End of Study (EoS): Date of the last testing/reading released of the Human Biological Samples, related to primary and secondary endpoints. EoS must be achieved no later than 8 months after Last Subject Last Visit (LSLV) (LSLV = Day 541, Month 18 in Phase II, formulation and schedule-finding). *If the completion of testing occurs prior the completion of the LSLV the latter date defines the end of study visit.*

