6.3.5.2. Phase II (Formulation and Schedule-finding)

This phase is partially blinded. Data in the 4 ABCWY groups will be collected in an observer-blind manner. To do so, study intervention(s) will be prepared and administered by qualified study personnel who will not participate in data collection, evaluation, review or the entry of any study endpoint (i.e. reactogenicity, safety, efficacy).

Data in the Control group will be collected in an open-label manner i.e. study participants, investigator and site staff personnel will be aware of the treatment administered as 2 study interventions are administered at Visit V1.

The laboratory in charge of the laboratory testing will be blinded to the treatment as well as to the subject number. There will be no link between the study intervention groups and the identity of the participant. In addition, for each sample, a different randomly selected

subject code will be used at each timepoint. This subject coding will prevent the testing laboratory personnel from linking the consecutive timepoints to a specific subject.

Refer to the SPM for additional information about details on study blinding.

6.3.5.3. *Unblinding*

(Amended 22 March 2022)

The participant, the site and sponsor personnel involved in the clinical evaluation of the participants will be unblinded to the treatment assigned at a Phase at completion of that particular Phase.

Refer to Section 4.4 for the definition of study completion per participant.

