6.6. Continued access to study intervention after the end of the study

(Amended 22 March 2022)

During the study conclusion visit/contact (Telephone T3 in Phase I, Visit V6 in Phase II, Formulation and Schedule-finding and Telephone T2/ **Telephone T3** in Phase II, Sourcing *[as per group allocation]*), the investigator will ask each participant/participant's parent(s)/LAR(s) if they are interested in participating/allowing the participant to join a booster study/long-term study. If a participant/participant's parent(s)/LAR(s) is/are not interested in joining the booster study/long-term study the reason for refusal will be documented, when available, in the participant's eCRF.

The investigator is encouraged to share the immunological assay results of non-responders with the study participants/participants' parent(s)/LAR(s).

It is the responsibility of the investigator to determine the medical care of the non-responder as per local/regional practices, such as re-vaccination.

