10.9.2. Glossary of terms

Adverse event:	Any untoward medical occurrence in a patient or clinical investigation participant, temporally associated with the use of a medicinal product, whether or not considered related to the medicinal product. An adverse event (AE) can therefore be any unfavourable and unintended sign (including an abnormal laboratory finding), symptom, or disease (new or exacerbated) temporally associated with the use of a medicinal product. For marketed medicinal products, this also includes failure to produce expected benefits (i.e. lack of efficacy), abuse or misuse.
Blinding:	A procedure in which 1 or more parties to the trial are kept unaware of the intervention assignment in order to reduce the risk of biased study outcomes. The level of blinding is maintained throughout the conduct of the trial, and only when the data are cleaned to an acceptable level of quality will appropriate personnel be unblinded or when required in case of a serious adverse event. For Phase I and Phase II Sourcing: In an observer-blind study, the participant, the site and sponsor personnel involved in the clinical evaluation of the participants are blinded while other study personnel may be aware of the treatment assignment. For Phase II Formulation and Schedule-finding: Partially-blind is to be used for study designs with different blinding levels between different groups, e.g. double-blinded consistency lots which are open with respect to the control group.
Certified copy:	A copy (irrespective of the type of media used) of the original record that has been verified (i.e. by a dated signature or by generation through a validated process) to have the same information, including data that describe the context, content, and structure, as the original.
Child in care:	A child who has been placed under the control or protection of an agency, organisation, institution or entity by the courts, the government or a government body, acting in accordance with powers conferred on them by law or regulation. The definition of a child in care can include a child cared for by foster parents or

living in a care home or institution, provided that the arrangement falls within the definition above. The definition of a child in care does not include a child who is adopted or has an appointed legal guardian.

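### Could sending immunological results to investigators as soon as they are ready undo the observer blind before the Phase is complete?

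*Protocol*

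**What the plan says.** **Release of results.** Protocol section 8.1.5 states "The immunological assay results will be communicated to the investigator when ready and available" and then refers to section 6.6 for the handling of non-responders. Section 6.6 says "The investigator is encouraged to share the immunological assay results of non-responders with the study participants". Neither section gives a date or a blinding condition.

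**Blinding.** For Formulation and Schedule-finding, section 6.3.5.2 says "Data in the 4 ABCWY groups will be collected in an observer-blind manner"; the Control group is open-label. Under section 6.3.5.3, participants and the site and sponsor staff who evaluate them "will be unblinded to the treatment assigned at a Phase at completion of that particular Phase". The glossary entry on blinding adds "The level of blinding is maintained throughout the conduct of the trial". Section 10.1.6 holds back each site's randomisation codes until the full statistical analysis is done.

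**Timing.** Section 4.4 defines the end of study by the last test result for primary and secondary endpoints, allows up to 8 months after the last visit for this, and adds "If the completion of testing occurs prior the completion of the LSLV the latter date defines the end of study visit". Note 1 to Figure 2 (section 4.1.2.1) says "Blood draw at Visit 6 Month 18 will be used only for assessment of tertiary objectives". Section 4.1.2.2 says "Refer to Section 9.4.6 for the planned interim analysis"; the content of that analysis is redacted.

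**The concern.** Read alone, section 8.1.5 makes readiness the only trigger for release, while section 6.3.5.3 makes completion of the Phase the trigger for unblinding. The first could come before the second: section 4.4 allows for testing to finish early, and the last draw that serves primary or secondary endpoints is at Visit 5, long before Visit 6.

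The results are not neutral about allocation. Two of the four blinded groups get their first investigational dose at Day 1 and two at Day 121, so the Day 31 sample is post-dose in one pair and pre-dose in the other. A site holding a participant's Day 1 and Day 31 titres might infer the schedule. Table 11 also lists Day 1 endpoints for one pair and Day 31 as the baseline for the other, so the set of timepoints reported could itself be a clue.

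At stake would be the investigator's judgement on events recorded after Day 211. SAEs, AESIs and AEs leading to withdrawal through Day 541 are a primary safety endpoint, and section 10.3.9.2 leaves causality of unsolicited events to that judgement.

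**Working it through.** The plan states no figure to reproduce here. The check compares the provisions and does some date arithmetic.

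**1. How long could results be ready before the last visit?** Inputs: planned days from Table 3 and windows from Table 4 (Visit 4 to Visit 5, 25 to 44 days; Visit 4 to Visit 6, 353 to 374 days).
- Planned gap: 541 − 211 = 330 days.
- Shortest: 353 − 44 = 309 days. Longest: 374 − 25 = 349 days.

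These are upper bounds, because assay turnaround is not given. Section 4.4 is conditional: it settles which date counts as end of study and does not predict early testing. It equally allows testing to run 8 months past the last visit. SAP section 10.1.3.10 says the LOD and LLOQ were still under evaluation when Amendment 5 was written (29 August 2023), which makes early release of hSBA results less likely.

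**2. How many participants are blinded?** From Table 13, with the group order of section 4.1.2.1: 206 + 206 = 412 on the 0,6-month schedule and 196 + 196 = 392 on the 0,2-month schedule, so 412 + 392 = 804 of 1000. This is the size of the blinded groups, not a count of people shown to be exposed.

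**3. What could a result reveal?** In the 0,2-month groups the doses fall at Day 121 and Day 181 (181 − 121 = 60 days), so Day 31 lies 121 − 31 = 90 days before dose 1. In the 0,6-month groups Day 31 is 30 days after dose 1. A rise from Day 1 to Day 31 would suggest the 0,6-month schedule. The signal is imperfect: section 5.1 admits people with one earlier MenACWY dose, so a raised Day 31 titre on its own may reflect old priming. How well results would identify the schedule cannot be estimated, since expected response rates are not readable. Formulation is not exposed by this route, because Day 31 separates schedules and not doses of vaccine.

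**4. What would that knowledge affect?**
- Control is open-label, so sites already know that every other participant is in an investigational group.
- By Day 181 both doses have been given under either schedule. After Day 211 the new information is only whether dose 1 was at Day 1 or Day 121.
- Solicited events are treated as related by definition (section 10.3.9.2), and the solicited and 30-day unsolicited windows are essentially over by Day 211.
- The readable safety endpoints are frequencies and percentages by group. Section 9.1.2 contains no hypothesis that compares schedules on safety.
- The superiority and non-inferiority endpoints come from a laboratory blinded to treatment and subject number, with a new random code for each timepoint (section 6.3.5.2).

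**5. Do the two rules conflict?** Section 8.1.5 does not say that results go out before unblinding, and it claims no exception to section 6.3.5.3. It points only to section 6.6, whose heading concerns the time after the end of the study and whose first paragraph is set at the study conclusion visit or contact. A general statement about sending results can be obeyed together with a specific blinding rule: results are released once they are ready and the Phase is unblinded.

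**6. Other parts of the study.** The last draw precedes the concluding contact by 150 days in Phase I and in each Sourcing schedule (211 − 61, 241 − 91, 361 − 211). Table 11 gives neither part a readable primary or secondary immunogenicity endpoint, and schedule is not blinded in Sourcing. The point is therefore confined to Formulation and Schedule-finding.

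**The case for a change.** The best case for an edit is that the protocol takes unusual care over this kind of leak elsewhere. Section 8.1.1.1 has everyone bled whether or not the sample will be tested, expressly to protect the blind. The laboratory cannot link a subject's timepoints, and randomisation codes are withheld until the full analysis. None of these provisions says when participant-level results may reach a site. A site that follows section 8.1.5 to the letter could receive them while section 6.3.5.3 still requires blinding, and one sentence would remove the doubt.

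Part of this stands. The readable text of sections 8.1.5 and 6.6 has no cross-reference to section 6.3.5.3, the quoted wording is exact, and the date arithmetic is right. What does not stand is the step from a missing cross-reference to a likely breach. Those same safeguards show what the sponsor intends, and because of the coding, results could reach a site by participant only after being re-linked outside the testing laboratory. The immunological read-out section and the interim-analysis section are redacted, and section 6.3.5.2 refers to the study procedures manual for further blinding detail. A release rule may sit in any of these, so its absence cannot be inferred.

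**Conclusion.** No change to the plan is needed. The wording leaves a gap that the study team can fill sensibly from the rest of the protocol: participant-level results follow the Phase-completion unblinding rule. A cross-reference from sections 8.1.5 and 6.6 to section 6.3.5.3 would be tidy if no release rule exists elsewhere, but no analysis depends on it.

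The size is bounded. At most, results could be available 330 days (309 to 349) before a participant's last visit and hint at schedule within groups totalling 804 people. No readable endpoint, test or selection criterion is shown to change. The conclusion rests on three assumptions: that section 6.3.5.3 governs because section 8.1.5 does not override it; that the redacted sections do not authorise participant-level release to sites before Phase completion; and that the redacted safety analyses contain no formal comparison of causality between schedules. If either of the last two proved wrong, the point would deserve a second look.
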